# Study objectives

- 1. To determine the feasibility of the designed research process in terms of the following:
  - a. Recruitment/retention of participants
  - b. Randomisation of the participants.
  - c. Logistics manpower, resources
- 2. To determine the feasibility and acceptability of the designed intervention in terms of the following:
  - a. Usage of the cups as a standardized measure of fluid intake
  - b. Usage of the fluid charts as a tool for behaviour change
  - c. The implementation process of the intervention
- 3. To determine the trend of the preliminary results in order to:
  - a. To estimate the treatment effect size of the experimental intervention
  - b. To calculate the sample size for the main evaluation randomized controlled trial.
- 4. To refine the research process and intervention design for the main evaluation randomized controlled trial.

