## Preliminary outcome measures

The outcomes will be assessed at the end of the two month period of data collection.

Several preliminary outcomes measures will be used to assess the trend of the preliminary results in order to determine the treatment effect size of the fluid chart. The two pilot study groups will be compared in terms of:

- 1. The hospitalization rates
- 2. The need for intravenous fluid treatment
- 3. The severity of haemoconcentration. Four surrogate endpoints were utilized to determine this, and they were as follows:
  - a. The mean peak haematocrit
  - b. The difference in haematocrit level between the values of clinic consultation 2 clinic consultation 1.
  - c. Those above the local cut off value of haematocrit indicative of plasma leakage.
  - d. Haematocrit fluctuation of 20% or more
- 4. With regards to assessing the severity of the platelet drop, two secondary endpoints were used:
  - a. The mean nadir platelet count
  - b. The difference in the platelet level between the values of clinic consultation 2 clinic consultation1.
- 5. The difference in the amount of oral fluid intake between the two groups.

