# **Statistical analysis**

All the data for this pilot study will be expressed either as the mean  $\pm$  standard deviation or as frequencies and proportions. Differences in data between the control and intervention group will be analysed using the Student's t test for continuous variables. The chi-squared test ( $\chi^2$  test) or the Fisher's exact test will be used for categorical variables, whichever is appropriate. A p value < 0.05 is considered as statistically significant. The statistical software utilised for the analysis is SPSS version 16.0 (SPSS Inc. Cary, NC).

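### The protocol applies an unadjusted p < 0.05 rule to nine overlapping endpoints in a pilot meant for estimation, and gives the estimates no measure of precision and the tests no exploratory label

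*Protocol*

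**What the plan says.** Study objectives, item 3a, gives the purpose as "To estimate the treatment effect size of the experimental intervention"; item 3b adds calculating the sample size of the main trial. Preliminary outcome measures repeats that the outcomes serve to find the size of the treatment effect, and lists the comparisons under "The two pilot study groups will be compared in terms of". There are nine:

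- hospitalization;
- need for intravenous fluid;
- haematocrit: "Four surrogate endpoints were utilized to determine this" (mean peak, change between the first two consultations, above the local cut-off, fluctuation of 20% or more);
- platelets: "two secondary endpoints were used" (mean nadir, change between the first two consultations);
- amount of oral fluid intake.

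None is named primary.

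Statistical analysis says data are expressed as mean and SD "or as frequencies and proportions". It continues: "Differences in data between the control and intervention group will be analysed using the Student's t test for continuous variables". For the rest, the chi-squared test "or the Fisher's exact test will be used for categorical variables, whichever is appropriate". Then comes the single threshold: "A p value < 0.05 is considered as statistically significant". The section mentions no confidence interval and no exploratory status for the tests.

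Estimated sample size describes a time-driven study of two months, with a minimum of 30 patients per group (60 in total) and an aim to recruit as many as possible.

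**The concern.** The analysis rule does not fit the objective. Sizing a main trial needs an estimated difference and a statement of how uncertain it is. A threshold test answers another question, and in a small sample it answers it poorly. A non-significant result leaves large effects open, and a significant one is, on average, too big.

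The results are the stated input to the main-trial sample size. If significance steers which endpoint is carried forward, or if an exaggerated point estimate is used without its interval, the main trial may be too small.

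**Working it through.** **Inputs from the protocol.** Threshold 0.05; nine endpoints (1 + 1 + 4 + 2 + 1 = 9); 1:1 allocation; at least 30 per arm. Study setting gives clinic admission percentages of 55.4%, 40% and 63.41% for the three months before recruitment. Estimated sample size gives a 16.4% default rate from an earlier study at the clinic.

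**Assumptions.** Two-sided tests (sidedness is not stated); standardised effects of 0.3 and 0.5 SD; admission of 50% v 35%. The effect sizes are illustrative and are not in the protocol.

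**The plan's own figure.** 2 x 30 = 60 agrees with the stated minimum. It cannot be rebuilt further, because no effect size, SD, power or precision target is given for it.

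**1. At least one false positive when there is no effect.** For independent tests: 1 - 0.95^9 = 0.370. The nine are not independent. The section Intravenous fluid drip counts every admitted patient as having received it, and the haematocrit endpoints share values. Simulation with equally correlated normal statistics gives:

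| Correlation | Chance of at least one p < 0.05 |
|---|---|
| 0 | 37% |
| 0.3 | 33% |
| 0.5 | 27% |
| 0.7 | 20% |
| 0.9 | 12% |

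So 37% is an upper reference value.

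**2. Power at 30 per arm.**
- Continuous outcome, t test with 58 degrees of freedom and non-centrality d x sqrt(30/2): at d = 0.5 power is 0.478. The smallest effect with 80% power is 0.74 SD.
- Hospitalization, 50% v 35%: SE = sqrt[(0.50 x 0.50 + 0.35 x 0.65)/30] = 0.126. Then 0.15/0.126 - 1.96 = -0.77, and power is about 0.22. The same formula gives about 0.39 at 60 per arm and 0.58 at 100.

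**3. Exaggeration.** Take estimates drawn from a normal distribution with SE sqrt(2/30) = 0.258 SD. Those with p < 0.05 overstate a true 0.3 SD effect about 2.2-fold on average, and a true 0.5 SD effect about 1.4-fold.

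**4. What this could do to the next trial.** At 30 per arm, a difference in admission near 50% reaches p < 0.05 only at about 1.96 x sqrt(2 x 0.25/30) = 0.253, or 25 points. If the truth is 15 points, a significant result in the right direction overstates it at least about 1.6-fold (25/15 = 1.67). With n per arm = (1.96 + 0.84)^2 x [p1(1 - p1) + p2(1 - p2)]/(p1 - p2)^2, planning on 50% v 25% gives about 55 per arm, while 50% v 35% needs about 167. At 55 per arm, power for the 15-point effect is about 36%.

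**5. What an interval would show.** The 95% half-width at 30 per arm is about 25 points for hospitalization (24.4 to 25.3 over rates of 40% to 63%), and 1.96 x sqrt(2/30) = 0.51 SD for a continuous outcome. With 16.4% default, 30 x 0.836 = 25 per arm, and these become about 27 to 28 points and 0.55 SD.

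**The case against.** **The plan does yield effect sizes.** A reader might infer that significance verdicts replace the estimates. The text does not support that. Objective 3a commits to estimation, and means, SDs and proportions by arm give the point difference and the SD or control rate. This stands; what is lacking is precision and an exploratory label.

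**Intervals may be in a SAP that is not shown.** True, and their absence alone would be no finding. But the significance rule is written in the protocol, and it is that rule which does not fit the objective.

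**No decision hangs on a p value.** A reader might infer that progression or the main-trial sample size will follow from significance. No section says so. The study is called exploratory in the Background and its outcomes preliminary. This stands, so step 4 shows what could happen, not what is planned. The general description still does not tell a reader how to take a p value below 0.05.

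**Sixty is a minimum.** Correct, and more patients raise power and narrow the intervals. The false-positive chance does not fall with sample size, and power for the assumed 15-point effect is still only about 58% at 100 per arm.

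**The admission rate is uncertain.** The clinic percentages include patients admitted at the first visit, whom the Exclusion criteria remove, so the rate in the trial may be lower. At 20% the half-width would be 1.96 x sqrt(2 x 0.20 x 0.80/30) = 0.202, or about 20 points, which is still wide.

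**Two further inferences fail.** That a significant result is probably false would need a prior probability of effect, which the protocol does not give. That a multiplicity correction is required does not follow either: for an estimation study the remedy lies in how results are reported.

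**Conclusion.** The concern holds in this form: the protocol fixes an unadjusted significance rule for nine overlapping endpoints in a pilot whose purpose is estimation, and neither conveys precision nor marks the tests as exploratory.

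At the minimum size the verdicts are unreliable both ways. The false-positive chance has 37% as its ceiling under independence and is about 20% to 33% at correlations of 0.7 to 0.3. Power is about 48% for 0.5 SD and 22% for 50% v 35%. Significant estimates are inflated about 1.4-fold to 2.2-fold for true effects of 0.5 and 0.3 SD.

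These figures rest on two-sided testing, full data on 30 per arm, illustrative effects and an assumed correlation structure. They do not show that the pilot will fail to produce effect sizes or that its sponsor will misuse p values. This is a cheap improvement, not a fatal flaw.

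**What to change.** In Statistical analysis, replace the significance sentence with: *For each outcome the between-group difference (mean difference or risk difference) is reported with its 95% confidence interval; any p values are exploratory and are not used to conclude effectiveness.*

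Add that the main-trial sample-size calculation takes the interval into account, not the point estimate alone, for example by showing the required size across a range of effects within it.

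This takes a sentence or two and needs no extra patients, data or procedures. The downside is that the pilot report can no longer claim statistical significance for any outcome.

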# Definitions, terminology and assumptions

#### Definitions

#### Thrombocytopenia

This is defined as a platelet count of < 150 x  $10^9$ g/L. This is the definition used by another Malaysian study .

## Severity of haemoconcentration:

#### Haematocrit fluctuation of 20% or more

This was calculated using the following standard formula:

Haematocrit fluctuation = (highest haematocrit – population baseline haematocrit) / population baseline haematocrit X 100%

The average population baseline haematocrit value for a 20 year old adult Malaysian male was 0.45 and for the average 20 year old Malaysian female was 0.38. These average population values were obtained and utilised with kind permission from [name] by personal communication based on her unpublished DENCO study data.

The author will use the average population baseline haematocrit rather than the individual patient's own values because no convalescent sample is routinely done for all the patients enrolled in this pilot study. Moreover, it has been shown by a prior study done in Vietnam which had correctly identified 94% of shocked patients as having capillary leak by utilising the local population mean haematocrit as the baseline for calculating the 20% fluctuation in haematocrit level.

Also, the length of patient follow-up varies from patient to patient depending on the attending doctor's assessment of the patient. This secondary endpoint is chosen as a measure for haemoconcentration based on the previous World Health Organization's guidelines for dengue, which included 20% fluctuation in haematocrit as one of the four diagnostic criteria for dengue haemorrhagic fever (DHF). A local Malaysian study also found a fluctuation of 20% haematocrit level to be highly associated with Dengue Haemorrhagic Fever (using the previous World Health Organization classification system).

## Above the local cut off value indicative of plasma leakage

This is measured by calculating the percentage of patients achieving and surpassing the local Malaysian population cut off value for haematocrit to suspect plasma leakage. According to a recent study done on the Malaysian population, the cut off value that had been validated for Malaysian males was 0.47, and for the Malaysian females was 0.40^44.

## Day of illness

Day 1 of illness is defined as the day of onset of fever. The subsequent day of illness uses day 1 of illness as a reference.

## Dengue phase of illness

The dengue phase of illness is based on the day of illness on recruitment into the study, which is as follows:

- The febrile phase is defined as day 1 of illness till day 3 of illness.
- The critical phase is from day 4 of illness to day 6 of illness.
- The recovery phase is defined as from day 7 onwards of illness.

# Patient diagnosis

The final diagnosis of the patients who are recruited into the study is defined as follows:

- The patient is defined as having dengue fever if the dengue IgM is positive in either the first sample or the second sample of dengue serology.
- Patients are defined as having probable dengue fever if the dengue IgG is positive regardless of the IgM.
- If both the dengue IgM and IgG are negative, then the patient will be given the diagnosis of other febrile illness.

## Body Mass Index (BMI)

In contrast to other infectious diseases, there is evidence to show that severe forms of dengue are more common in well-nourished children. Grade 2 or 3 protein-calorie malnutrition has been shown to be protective against severe dengue vasculopathy. For this reason, BMI is included in the clinical data to be captured during the recruitment of participants into this study.

The Body Mass Index (BMI) is classified using the Malaysian Clinical Practice Guidelines for Obesity:

- BMI < 18.4 was defined as underweight
- BMI of 18.5 22.9 was defined as normal
- BMI of 23.0 27.4 was defined as pre-obese
- BMI of 27.5 34.9 was defined as obesity class I
- BMI of 35.0 39.9 was defined as obesity class II
- BMI > 40.0 as obesity class III

# Types of fluid

The types of fluid that are consumed by the patients were defined as follows:

- Water plain water.
- Isotonic drinks meant either commercially available isotonic drinks or the oral rehydration salts which were made up to be isotonic drinks.
- Juice meant any type of fruit juice.
- Milk meant any type of milk.
- Barley meant either the barley drinks that are commercially available or those that were home-made.
- Caffeinated drinks meant any drinks containing caffeine, for example coffee, tea or nescafe.
- Nourishing fluids included the following: alpha lipid drink, Horlicks, vitagen, soup, honey drink, milo drink, and yoghurt drink.
- Semisolids included the following: oats, and porridge.
- Cordial drinks consisted of any type of cordial and carbonated drinks.
- Soya drink meant drinks made from soya bean, either commercially available or home-made
- Home remedies this included a variety of drinks, including home made liver soup, herb drinks, chloro 'B', home-made dates juice, home-made honey and lime drink, home-made 'assam jawa' drink.

## Amount of fluid in the cups used for the intervention group

Each of the uniform sized cups used in the intervention group contains up to 175 ml of fluids. The principal researcher measures the amount of fluid a cup will contain by filling the cup with water using a syringe to estimate the amount.

## Defaulted follow-up and drop out

The term defaulted follow-up means that the patient comes to see the researcher at least once after recruitment into the study. This is not interchangeable with the term drop out, meaning the patient is only seen once by the researcher or the assistants during recruitment, and does not return to see the research team at all after recruitment.

## Assumptions

The author has to make several assumptions while conducting this research.

## Intravenous fluid drip

If the patient was admitted to hospital after recruitment, it is assumed that the patient would have received intravenous fluid drip.

## Conversions used for calculation of total fluid intake

The author has to make several assumptions to ease the calculation of total oral fluid intake, due to the very nature of the data collected from the patients. It is found that patients used a variety of containers of varying shapes and sizes for their daily oral fluid intake.

- For the control group, each glass that the patient reported at home contained 175 ml of fluids, which is equivalent to the amount of fluid contained in the cup used in the intervention group.
- A regular, standard sized mug contains 250 ml of fluids (the principal researcher measured the amount of fluid a mug of such size will contain by filling the mug with water using a syringe to estimate the amount).
- One large cup used by the patient at home is equivalent to one mug, which contains 250ml of water.
- One plastic bag of drinks bought from the hawker stall is equivalent to three cups of water
- One small packet drink contains 250 ml of fluid (as is written on the packet drink itself).
- One can drink contains 325 ml of fluid (as is written on the can itself).
- One small bottle of mineral water contains 500 ml of fluid (as is stated on the bottle label itself).
- One big bottle of drinks contain 1000 ml of fluid (as is stated on the bottle label itself).
- One large bottle of drinks contain 1500 ml of fluid (as is stated on the bottle label itself).
- One jug of water contains 1000 ml of fluid

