Although there has been some evidence that encouraging oral fluid intake might decrease the morbidity of dengue infections, it is still uncertain whether oral fluid intake exerts a protective effect against the progression from non-severe to severe dengue . It is still unknown whether increasing oral fluid intake would alter the progression of dengue in terms of the degree of haemoconcentration and the fall in platelets.

Both of these parameters are routinely used for monitoring of both outpatients and hospitalized suspected dengue patients. Primary healthcare providers monitor these parameters very closely. Coupled with the clinical condition, primary physicians determine the necessity for hospital admission. Moreover, both these parameters constitute part of the warning signs mentioned in the WHO 2009 guidelines. However, it is still unknown whether increasing oral fluid intake in dengue patients will improve the mortality of dengue by lessening its progression or severity.

From the two studies looking at the effects of oral fluid intake, more questions arise. Should there be an association between oral fluid intake and the risk of hospitalization for dengue patients, an accurate estimation of the amount of fluid needed daily to achieve this effect is not known. The Nicaragua study collected data by retrospectively asking the patients how many glasses of fluid was ingested during the previous 24 hours. The findings are subject to recall bias. Moreover, there is a great variation in size of the glasses and cups used by the general population. Therefore an accurate estimate of the amount of fluid ingested daily could not be obtained.

The Taiwan study did not collect any data on the amount nor the type of oral fluids consumed by the patients in their oral hydration group. The only study that had some data on the types of fluids consumed by their patients was the study done in Nicaragua. Thus, little is known on the kinds of fluids that would be ideal for oral hydration in dengue patients. Such knowledge would greatly aid the primary healthcare members as well as other clinicians in providing accurate, evidence based advice regarding the quantity and types of fluids for dengue patients to consume in order to avoid hospitalization.

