#### Method of intervention received by the control group only

Apart from this, the control group will be asked their twenty four hour fluid recall. This means that the patient will be asked to give an estimate of how much fluid they have drunk in the twenty four hours prior to the current consultation with the researcher or the trained research assistants.

This estimate will be given by the patients in terms of how many litres or millilitres of fluid they drank, how many glasses (small or large sized glasses or mugs), or how many bottles of drinks they had (500ml size, 1 litre size, or 1.5 litre size), or how many packet drinks they had. Details on what type of fluids is consumed orally will be obtained. This information will be obtained during recruitment of the patient, and on each subsequent follow-up.

One should take note that no fluid chart or cup will be given to the control group participants.

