## Method of intervention received by the intervention group

The patients assigned to the intervention group will be given a plastic cup of uniform size, along with a twenty four hour fluid chart. These patients will be instructed to use the cup for drinking any form of fluid they wish to consume for the duration of their participation in the study. Verbal instructions will be given on how to fill in the various details required on the fluid chart regarding their oral fluid consumption.

This will be done over the next twenty four hours or until they come for their next follow-up consultation at the clinic. If the next clinic follow-up will be given at the interval of a few days after the preceding consultation, then the researcher or the trained research assistant will provide enough fluid chart forms for the patient to fill until the next consultation.

The patient will be instructed to write down the amount of fluids they drank according to the time that they consumed the fluids in the second column. The patients will be instructed to record the type of fluids they drink in the third column. The patient will only fill the last column if they received any intravenous fluid drip over the next twenty four hours. They are to record the amount of bottles of fluid they receive intravenously.

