## **Control group**

The researcher or the research assistant will obtain data regarding the twenty four hour fluid recall and the types of fluids consumed for each subsequent follow-up visit.

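### Oral fluid intake is recorded by a different method in each arm, so the between-arm difference mixes what patients drank with how it was recorded, in unknown direction and size

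*Protocol*

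**What the plan says.** The fifth item under Preliminary outcome measures is "The difference in the amount of oral fluid intake between the two groups". That section says the measures are used to "assess the trend of the preliminary results in order to determine the treatment effect size of the fluid chart". The Study objectives add that the preliminary results serve to calculate the sample size of the main trial.

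The intake data come from two different procedures:

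- **Intervention arm** (Method of intervention received by the intervention group): "The patient will be instructed to write down the amount of fluids they drank according to the time that they consumed the fluids". Patients drink from a uniform cup and get enough charts to last until the next visit. The section on the amount of fluid in the cups puts the cup at up to 175 ml, measured by syringe. Under Follow-up, staff go through the entries with the patient.
- **Control arm** (Method of intervention received by the control group only): "the patient will be asked to give an estimate of how much fluid they have drunk in the twenty four hours prior". Answers may be in litres or millilitres, small or large glasses or mugs, bottles or packets. On timing: "This information will be obtained during recruitment of the patient, and on each subsequent follow-up". The Follow-up section repeats that staff "will obtain data regarding the twenty four hour fluid recall and the types of fluids consumed". Controls get neither chart nor cup.

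The conversion rules then state: "For the control group, each glass that the patient reported at home contained 175 ml of fluids". Mugs, large cups, packets, cans, bottles and jugs have their own volumes.

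The Follow-up section headed Both groups lists blood results and temperature as the common data. It lists no fluid measure.

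**The concern.** Intake is the outcome closest to the research question, which asks whether the chart improves drinking. Its between-arm contrast is built from two instruments that differ in three ways at once: timing (as it happens against from memory), window (every day up to the next visit against the last 24 hours) and container (a supplied cup against whatever is at home). Randomisation does not protect against this, because the instrument is assigned together with the treatment.

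The Background faults the earlier observational study for recall bias and because "there is a great variation in size of the glasses and cups used by the general population". In that study everyone was measured alike. Here the same weaknesses are confined to one arm, where they become differential error.

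An artefact could produce a difference with no change in drinking, or hide a real one. Recruiting more patients would not remove it. If intake is the outcome used to size the main trial, the artefact goes into that calculation.

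**Working it through.** **No figure to reproduce.** The minimum of 30 per arm is not derived from an effect, a standard deviation or a power, so the check is a sensitivity calculation.

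**Inputs from the protocol:** control glass 175 ml; mug or large cup 250 ml; 30 per arm; p < 0.05; Student's t test.

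**Assumptions (not in the documents):** true home glass *g* of 150, 200 or 250 ml; *k* = 5 or 10 drinks a day reported as glasses; SD of daily intake 500, 750 or 1,000 ml; two-sided test.

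**Step 1, error in the glass-reported part of control intake.** Relative error = 175/*g* − 1. With equal true drinking and no other error, the artefact in the difference (intervention minus control) is *k*(*g* − 175) ml a day.

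| True glass | Relative error in control record | Artefact, *k* = 5 | Artefact, *k* = 10 |
|---|---|---|---|
| 150 ml | 175/150 − 1 = +16.7% | −125 ml | −250 ml |
| 200 ml | 175/200 − 1 = −12.5% | +125 ml | +250 ml |
| 250 ml | 175/250 − 1 = −30.0% | +375 ml | +750 ml |

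The sign reverses below 175 ml. Drinks reported by mug, can, packet, bottle or litre are outside this table. Recall error touches all control intake, but the documents give nothing from which to size it.

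**Step 2, chance of p < 0.05 with no true difference, 30 per arm.** SE = SD × √(2/30). For an artefact *b*, the probability is Φ(*b*/SE − 1.96) + Φ(−*b*/SE − 1.96), by normal approximation. Example: *b* = 250 and SD = 750 give SE = 193.6, *b*/SE = 1.29, probability 25%.

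| Artefact (either sign) | SD 500 | SD 750 | SD 1,000 |
|---|---|---|---|
| 125 ml | 16% | 10% | 8% |
| 250 ml | 49% | 25% | 16% |
| 375 ml | 83% | 49% | 31% |

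**Step 3, main trial size if intake were the outcome that sets it.** Per arm, *n* = 2(1.96 + 0.84)² × SD²/δ². Take an assumed true effect of 300 ml, SD 750 ml and 80% power.

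| Artefact | Apparent effect δ | *n* per arm |
|---|---|---|
| none | 300 ml | 99 |
| +125 ml | 425 ml | 49 |
| +375 ml | 675 ml | 20 |
| −125 ml | 175 ml | 289 |

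Steps 2 and 3 show how sensitive the result is. They do not predict what this pilot will find.

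**The case against.** The strongest reply is that this is a feasibility pilot whose Aim names 24-hour recall as the comparator. Use of the cup as a standard measure is itself under test, refining the process is an objective, and intake is the last of five preliminary outcomes. No passage says which outcome will size the main trial. This stands as a limit: transfer of the artefact into that calculation is possible, not established. It does not answer the point, because estimating the effect size is also a stated objective, and naming recall as comparator explains the design without making the two measures comparable. A separate analysis plan, if one exists, cannot recover recall that was never taken in the intervention arm.

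Several stronger readings are tempting, and the documents do not support them:

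- **The bias can only lower control intake.** 175 ml is the smallest entry in the conversion list, but that says nothing about real glasses. Small glasses are collected too, and a glass under 175 ml is overstated.
- **A spurious gain of up to 1,000 ml a day.** That needs 8 drinks a day, all reported as glasses and all truly 300 ml: 8 × (300 − 175) = 1,000. The protocol converts mugs and large cups at 250 ml, and other containers separately. Whether a large glass counts as 175 or 250 ml is unclear. The share of intake reported by glass is not given.
- **Under-recall adds to the gap.** The Background says only that recall is biased. Controls who have just been read drinking advice may over-report, and diaries can miss entries.
- **Method matters as much as the intervention.** Without a true glass volume, SD or effect, the two cannot be ranked.
- **The small cup may reduce drinking**, with five cups (5 × 175 = 875 ml) taken as the advised five glasses. This is conjecture about behaviour, and the chart would show it.
- **The intervention arm has no baseline intake.** The visible text does not specify one, but the data collection form and flow diagram are not shown.

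**Conclusion.** The point holds in this form: for the intake outcome, method is fully aligned with arm and the visible text describes no common measure. The planned difference therefore confounds drinking with recording, and neither the direction nor the size of the bias can be known from the data to be collected.

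The only quantifiable part concerns drinks reported as glasses: control intake understated by 12.5% or 30% if the true glass is 200 or 250 ml, overstated by about 17% if it is 150 ml. All three volumes are assumptions. Recall error is additional, in either direction.

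Hospitalisation and laboratory outcomes are not affected by this measurement difference, and the feasibility and acceptability objectives stand without it. The defect needs correcting before recruitment if intake is to inform an effect size, because the missing data cannot be obtained afterwards.

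**What to change.** 1. Take the same 24-hour recall in both arms, with the same form, staff and container conversions, at recruitment before allocation and at every visit.
2. Make that recall the between-arm measure for the intake outcome, adjusted for recruitment recall. Keep the chart as the intervention and as an adherence record.
3. Show the 175 ml study cup at the booth and ask how many such cups the patient's own glass holds, instead of assuming 175 ml. State how a large glass is converted.
4. Add a sensitivity analysis of glass volume in both directions, for example 150, 200 and 250 ml.

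The cost is a few minutes per intervention-arm visit, a sample cup at the booth and one extra table. There are two limitations to state in the protocol. Recall by patients who have just kept a chart may still be more accurate than recall by controls, and staff are unblinded, so some differential error remains. The contrast also becomes chart plus recall against recall, since the protocol treats recall as the control procedure.
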